9.5.3. Suicide-Related Thoughts and Behaviors

Suicidal ideation, suicidal behavior, and non-suicidal self-injurious behavior based on the C-SSRS will be summarized by treatment group. For each of the following events, the number and percentage of patients with the event will be enumerated by treatment: completed suicide, non-fatal suicide attempt, interrupted attempt, aborted attempt, preparatory acts or behavior, active suicidal ideation with specific plan and intent, active suicidal ideation with some intent to act without specific plan, active suicidal ideation with any methods (not plan) without intent to act, non-specific active suicidal thoughts, wish to be dead, and non-suicidal self-injurious behavior.

In addition, the number and percentage of patients who experienced at least one of the composite measures during Study Period III, Study Period IV, and Study Period V separately will be presented and compared. These include suicidal acts (completed suicide and nonfatal suicidal attempts), suicidal behavior (suicidal acts, interrupted attempts, aborted attempts, and preparatory acts or behavior), treatment-emergent suicidal ideation or treatment-emergent suicidal behavior.

The Fisher's exact test will be used for treatment comparisons.

9.5.4. Vital Signs and Weight

Vital signs collected during the study include systolic and diastolic blood pressure, pulse, and temperature. Blood pressure and pulse measurements will be taken when the patient is in a sitting position. Three measurements of sitting blood pressure and pulse will be collected. The 3 sitting blood pressure and pulse measurements will be averaged and used as the value for that visit for analysis.

The incidence rates of patients with treatment-emergent vital sign and weight changes based at any time postbaseline and at LOCF endpoint will be assessed using Fisher's exact test. Specific criteria for treatment emergent definition will be documented in the SAP.

9.5.5. Electrocardiogram Intervals and Heart Rate

Analyses of corrected QT interval will be calculated using two correction formulas. The QTcF (measured in milliseconds [msec]) will be calculated with Fridericia's formula as QT/RR ^{1/3}. The Lilly Large Clinical Trial Population Based QT Correction (QTcR) (msec) will be calculated with the formula as QT/RR ^{0.413}. The number and percent of patients meeting criteria for treatment-emergent abnormalities in ECG intervals (pulse rate [PR], QRS, QTcF, and QTcR) and heart rate at any time during study will be summarized. Treatment group comparisons will be performed using the Fisher's exact test.

9.5.6. Laboratory Tests

The incidence rates of patients with treatment-emergent abnormal, high, or low laboratory values at any time postbaseline and at LOCF endpoint will be assessed using the Fisher's exact tests for each laboratory test.

Patients will be defined as having a treatment-emergent low value if they have all normal or high values at baseline, followed by a value below the lower reference limit at any postbaseline visit. Patients with all normal or high values at baseline (no low values) will be included in the analysis of treatment-emergent low laboratory values. Patients will be defined as having a treatment-emergent high value if they have all normal or low values at baseline, followed by a value above the upper reference limit at any postbaseline visit. Patients with all normal or low values at baseline (no high values) will be included in the analysis of treatment-emergent high laboratory values.

For analytes simply classified as normal or abnormal, patients will be defined as having a treatment-emergent abnormal value if they have all normal values at baseline, followed by an abnormal value at any postbaseline visit. Patients with all normal values at baseline will be included in the analysis of treatment-emergent abnormal laboratory values.

9.7. Other Analyses

9.7.1. Health Economics

The change from baseline for the double-blind treatment phase and for the open-label treatment and post-treatment follow-up phases for MSQ v2.1 (Role Function-Restrictive, Role Function-Preventive, Emotional Function, and total score) and MIDAS (item scores and total score) will be analyzed. In addition, categorical analyses will be performed. Changes in healthcare resource utilization and employment status will also be evaluated. Details are summarized in the SAP.

9.7.2. Immunogenicity Analysis

Refer to the SAP for details.

9.7.3. Subgroup Analyses

Subgroup analyses will be performed for primary efficacy measure (change from baseline on number of migraine headache days) separately for each of the subgroup populations listed in Table CGAI.4. Subgroup analyses will be conducted only for the ITT patients in Study Period III.

Each of the subgroup analyses for the primary measure of change from baseline in the number of migraine headache days will be conducted using MMRM. The same MMRM model described in Section 9.4.1 will be used with terms of subgroup, subgroup-by-treatment, subgroup-by-month, and subgroup-by-treatment-by-month interactions added as additional covariates.

Table CGAI.4. Definition of Subgroup Variables

Subgroup Variable	Categories
• Sex	Male, female
• Racial Origin (combine those with less than	American Indian / Alaskan Native
10%)	Asian
	Black / African American
	Native Hawaiian / Pacific Islander
	White
	Multiple
• Ethnicity	Hispanic or Latino Not Hispanic or Latino
Region	North America, Europe, Other
Treatment-resistant status	Treatment-resistant status about whether a patient has failed 2 or more prophylactic treatments (Yes or No)
Concurrent preventive treatment use	Yes or No
Medication overuse	Yes versus No
Having aura or not (during baseline period)	Yes or No
Baseline anti-drug antibody status	Any confirmed positive anti-drug antibody at baseline (Yes versus No)
Neutralizing anti-drug antibody status	Any positive neutralizing anti-drug antibody time point (Yes versus No) – note that neutralizing anti-drug antibody assays are performed only on confirmed-positive anti-drug antibodies.
 Treatment-emergent anti-drug antibody status 	Any treatment-emergent anti-drug antibody (Yes versus No)

9.8. Interim Analyses

Two interim analyses are planned for this trial. The first interim analysis will occur during Study Period III (double-blind treatment); this may result in increasing the sample size or stopping the trial for futility. Details will be documented in the Statistical Analysis Center SAP, the ERB supplement and the DMC Charter.

The second interim analysis will be conducted after all patients have had the opportunity to complete Study Period III, and thus will be the final analysis of the primary efficacy endpoint.

To minimize the potential bias that results from performing an interim analysis, the first interim analysis for this study will be conducted under the auspices of an independent Statistical Analysis Center and DMC.

Only the DMC is authorized to evaluate unblinded interim efficacy and safety analyses (prior to the completion of the double-blind treatment phase). Study sites will receive information about interim results ONLY if they need to know for the safety of their patients.

Additional interim analyses may be conducted in support of regulatory submissions if necessary.

Unblinding details are specified in the unblinding plan section of the SAP or a separate unblinding plan document.

10. Study Governance Considerations

10.1. Regulatory and Ethical Considerations, Including the Informed Consent Process

10.1.1. Informed Consent

The investigator is responsible for ensuring:

- that the patient understands the potential risks and benefits of participating in the study
- that informed consent is given by each patient. This includes obtaining the appropriate signatures and dates on the ICF prior to the performance of any protocol procedures and prior to the administration of investigational product.
- answering any questions the patient may have throughout the study and sharing in a timely manner any new information that may be relevant to the patient's willingness to continue his or her participation in the trial.

10.1.2. Ethical Review

The investigator must give assurance that the ERB was properly constituted and convened as required by International Conference on Harmonisation (ICH) guidelines and other applicable laws and regulations.

Documentation of ERB approval of the protocol and the ICF must be provided to Lilly before the study may begin at the investigative site(s). Lilly or its representatives must approve the ICF, including any changes made by the ERBs, before it is used at the investigative site(s). All ICFs must be compliant with the ICH guideline on GCP.

The study site's ERB(s) should be provided with the following:

- the current IB and updates during the course of the study
- informed consent form
- relevant curricula vitae

10.1.3. Regulatory Considerations

This study will be conducted in accordance with:

- consensus ethics principles derived from international ethics guidelines, including the Declaration of Helsinki and Council for International Organizations of Medical Sciences (CIOMS) International Ethical Guidelines
- applicable ICH GCP guidelines
- applicable laws and regulations

Some of the obligations of the sponsor will be assigned to a third-party organization (TPO).

10.1.4. Investigator Information

Investigators in this clinical trial should be neurologists, headache specialists, or other specialists with experience in headache clinical trials and treating migraine headache patients.

10.1.5. Protocol Signatures

The sponsor's responsible medical officer will approve the protocol, confirming that, to the best of his or her knowledge, the protocol accurately describes the planned design and conduct of the study.

After reading the protocol, each principal investigator will sign the protocol signature page and send a copy of the signed page to a Lilly representative.

10.1.6. Final Report Signature

The clinical study report (CSR) coordinating investigator will sign the final CSR for this study, indicating agreement that, to the best of his or her knowledge, the report accurately describes the conduct and results of the study.

An investigator selected by the study team will serve as the CSR coordinating investigator. If this investigator is unable to fulfill this function, another investigator will be chosen by Lilly to serve as the CSR coordinating investigator.

The sponsor's responsible medical officer and statistician will approve the final CSR for this study, confirming that, to the best of his or her knowledge, the report accurately describes the conduct and results of the study.

10.2. Data Quality Assurance

To ensure accurate, complete, and reliable data, Lilly or its representatives will do the following:

- provide instructional material to the study sites, as appropriate
- sponsor start-up training to instruct the investigators and study coordinators. This
 training will give instruction on the protocol, the completion of the eCRFs, and
 study procedures.
- make periodic visits to the study site
- be available for consultation and stay in contact with the study site personnel by mail/e-mail, telephone, and/or fax
- review and evaluate eCRF data and use standard computer edits to detect errors in data collection
- conduct a quality review of the database

In addition, Lilly or its representatives will periodically check a sample of the patient data recorded against source documents at the study site. The study may be audited by Lilly or its representatives, and/or by regulatory agencies at any time. Investigators will be given notice before an audit occurs.

To ensure the safety of participants in the study, and to ensure accurate, complete, and reliable data, the investigator will keep records of ECGs, laboratory tests, clinical notes, and patient medical records in the patient files as original source documents for the study according to retention requirements as outlined by the ICH guidelines. If requested, the investigator will provide the sponsor, applicable regulatory agencies, and applicable ERBs with direct access to original source documents.

10.2.1. Data Capture System

An electronic data capture system will be used in this study. The site maintains a separate source for the data entered by the site into the sponsor-provided electronic data capture system.

Some or all of a patient's data will be directly entered into the eCRF at the time that the information is obtained. In instances where direct data entry is not used, the site will maintain source documentation in the trial files, and the patient's data will be transcribed into the eCRF. Any data for which the eCRF will serve as the source document, or any other data not entered directly into the eCRF, will be identified and documented by the site in the site's trial file. For data handled by a data management TPO, eCRF data and some or all data that are related will be managed and stored electronically in the TPO system. Subsequent to the final database lock, validated data will be transferred to the sponsor. For data handled internally, eCRF data and some or all data that are related will be managed by the sponsor and stored electronically in the sponsor's system.

In this study, patient migraine headache data will be collected directly via an ePRO diary as part of an ePRO/Clinical Outcome Assessment (COA) system. Patient-rated scales/questionnaires will be collected directly via an ePRO tablet device at each visit. Data entered into the ePRO/COA system will serve as the source data.

If ePRO/COA records are stored at a third-party site, investigator sites will have continuous access to the source documents during the study and will receive an archival copy at the end of the study for retention.

Any data for which the ePRO/COA instrument record will serve to collect source data will be identified and documented by each site in that site's study file.

Case report form data will be encoded and stored in a clinical trial database. Data managed by a central vendor, such as laboratory test data or ECG data, will be stored electronically in the central vendor's database system. Data will subsequently be transferred from the central vendor to the Lilly data warehouse. Data from complaint forms submitted to Lilly will be encoded and stored in the global product complaint management system.

10.3. Study and Site Closure

10.3.1. Discontinuation of Study Sites

Study site participation may be discontinued if Lilly or its designee, the investigator, or the ERB of the study site judges it necessary for medical, safety, regulatory, or other reasons consistent with applicable laws, regulations, and GCP.

Appendix 1. Abbreviations and Definitions

Term	Definition
AE	adverse event: Any untoward medical occurrence in a patient or clinical investigation subject administered a pharmaceutical product that does not necessarily have a causal relationship with this treatment. An adverse event can therefore be any unfavorable and unintended sign (including an abnormal laboratory finding), symptom, or disease temporally associated with the use of a medicinal (investigational) product, whether or not related to the medicinal (investigational) product.
complaint	A complaint is any written, electronic, or oral communication that alleges deficiencies related to the identity, quality, purity, durability, reliability, safety or effectiveness, or performance of a drug or drug delivery system.
enroll	The act of assigning a patient to a treatment. Patients who are enrolled in the trial are those who have been assigned to a treatment.
enter	Patients entered into a trial are those who sign the informed consent form directly or through their legally acceptable representatives.
ePRO	electronic patient-reported outcomes
interim analysis	An interim analysis is an analysis of clinical study data, separated into treatment groups, that is conducted before the final reporting database is created/locked.
investigational product	A pharmaceutical form of an active ingredient or placebo being tested or used as a reference in a clinical trial, including products already on the market when used or assembled (formulated or packaged) in a way different from the authorized form, or marketed products used for an unauthorized indication, or marketed products used to gain further information about the authorized form.
ІТТ	intent to treat: The principle that asserts that the effect of a treatment policy can be best assessed by evaluating on the basis of the intention to treat a patient (that is, the planned treatment regimen) rather than the actual treatment given. It has the consequence that patients allocated to a treatment group should be followed up, assessed, and analyzed as members of that group irrespective of their compliance to the planned course of treatment.
IWRS	interactive web-response system
SAE	serious adverse event
TEAE	treatment-emergent adverse event: Any untoward medical occurrence that either occurs or worsens at any time after treatment baseline and that does not necessarily have to have a causal relationship with this treatment.

Appendix 2. Schedule of Activities

Schedule of Activities, Protocol I5Q-MC-CGAI (Double-Blind Treatment Phase)

Study Period (SP)	SP I Screening	SP II Prospective Baseline	SP III Double-Blind Treatment							
(Target) Interval (days) since previous visit			30-45	14	16	30	30			
Allowable range (days) between visits	3-45	30-40 ^a								
Interval allowance (days)				+/- 1	+/- 3	+/- 2	+/- 2			
Visit	1	2	3	4 ^b	5	6	7			
Month			0	0.5	1	2	3			
Assessments and Procedures										
Informed consent	X									
Inclusion/exclusion	X	X	X							
Demographics	X									
Physical examination	X									
Neurological examination ^c	X						X			
Height	X									
Weight	X						X			
Waist/hip circumference	X									
Medical history	X									
Pre-specified migraine history		X								
Substance use	X									
ECG ^d	X		X				X			
Vital signs ^e	X		X		X	X	X			
Adverse events	X	X	X	X	X	X	X			
Concomitant medications	X	X	X		X	X	X			
ePRO training		X								
ePRO daily patient entries		X	X	X	X	X	X			
Patient training video			X							

Clinical Laboratory Tests an	nd Sampling (Sahadula					
Hematology	X	Schedule 	X				X
Clinical chemistry	X		X^{f}				X ^f
HDL	X		X ^e				Xe
HbA1c	Λ		X				X
Fasting insulin/							
fasting C-peptide			X^{e}				X ^e
Urinalysis ^g	X		X				X
Serum Pregnancy (for women of childbearing potential) or FSH at V1 (all other female patients) ^h	X						X
Urine pregnancy ^h			X		X	X	
Urine drug screen	X						
Immunogenicity ⁱ			X	X	X	X	X
Biomarker storage sample ⁱ	X	X	X		X		
CCI							
PK blood sample ⁱ				X	X	X	X
CCI							
RNA			X				X
Study drug administered ^j			X		X	X	X (if continuing to OLE)
Scales, Questionnaires, and	Outcome Mea	asures					
MIDAS			X				X
MSQv2.1			X		X	X	X
HCRU/Employment			X		Х	X	X
Status					23	7.	71
Non-migraine chronic pain assessment ^k			X				X
PGI-S			X		X	X	X
1 01 5							
PGI-I					X	X	X

Schedule of Activities, Protocol I5Q-MC-CGAI (Open-Label and Post-Treatment Phases)												
Study Period (SP)			SP V Post-treatment									
(Target) Interval (days) since previous visit	30	30	30	30	30	30	30	30	30	60	60	
Interval allowance (days)	+/- 2	+/- 2	+/- 2	+/- 2	+/- 2	+/- 2	+/- 2	+/- 2	+/- 2	+/- 5	+/- 5	ET
Visit	8	9	10	11	12	13	14	15	16	17	18	
Month	4	5	6	7	8	9	10	11	12	14	16	
Assessments and Pro	ocedures											
Weight			X			X			X		X	X
Neurological examination ^c			X			X			X		X	X
ECG ^d			X						X		X	X
Vital signs ^e	X	X	X	X	X	X	X	X	X	X	X	X
Adverse events	X	X	X	X	X	X	X	X	X	X	X	X
Concomitant medications	X	X	X	X	X	X	X	X	X	X	X	X
ePRO daily patient entries	X	X	X	X	X	X	X	X	X	X	X	X
Clinical Laboratory	Tests and	Sampling S	chedule									
Hematology			X			X			X		X	X
Clinical chemistry			X ^f			X ^f			X ^f		X ^f	X^{f}
HDL			X ^f			X ^f			X^{f}		X ^f	X^{f}
HbA1c			X			X			X		X	X
Fasting insulin/ fasting C-peptide			X^{f}			X^{f}			X^{f}			X^{f}
Urinalysis ^g			X			X			X		X	X
Serum Pregnancy												
(for women of childbearing potential) ^h									X		X	X

Study Period (SP)			SP V Post-treatment									
(Target) Interval (days) since previous visit	30	30	30	30	30	30	30	30	30	60	60	
Interval allowance (days)	+/- 2	+/- 2	+/- 2	+/- 2	+/- 2	+/- 2	+/- 2	+/- 2	+/- 2	+/- 5	+/- 5	ET
Visit	8	9	10	11	12	13	14	15	16	17	18	
Month	4	5	6	7	8	9	10	11	12	14	16	
Urine pregnancyh	X	X	X	X	X	X	X	X				
Immunogenicity ⁱ	X	X	X			X			X		X	X
Biomarker storage sample ⁱ			X						X		X	X
CCI												
PK blood sample ⁱ	X	X	X			X			X		X	X
Study drug ^j	X	X	X	X	X	X	X	X				
Scales, Questionnair	es, and Ou	tcome Mea	sures									
MIDAS			X			X			X		X	X
MSQv2.1	X	X	X	X	X	X	X	X	X	X	X	X
HCRU/ Employment Status	X	X	X	X	X	X	X	X	X	X	X	X
Non-migraine chronic pain assessment ^k			X						X			X
PGI-S	X	X	X	X	X	X	X	X	X	X	X	X
PGI-I			X			X			X			X
C-SSRS/SHSF, SHFU ¹	X	X	X	X	X	X	X	X	X	X	X	X

Abbreviations: CGRP = Calcitonin-gene related peptide; C-SSRS = Columbia-Suicide Severity Rating Scale; ECG = electrocardiogram; ePRO = electronic patient reported outcome; ET = early termination; FSH = follicle stimulating hormone; HbA1c = hemoglobin A1C; HDL = high density lipoprotein; MIDAS = Migraine Disability Assessment test; MSQ (v2.1) = Migraine Specific Quality of Life Questionnaire; OLE = open-label extension; PGI-I = Patient Global Impression of Improvement; PGI-S = Patient Global Impression of Severity; PK = pharmacokinetics; RNA = ribonucleic acid; SHSF = Self-harm supplement form; SHFU = Self-harm follow-up form; V1 = Visit 1.

Note: Selected tests may be obtained in the event of a treatment-emergent hepatic abnormality and may be required in follow-up with patients in consultation with the Lilly, or its designee, clinical research physician. See Appendix 4 for more details regarding specific hepatic monitoring tests. If the patient has discontinued the trial and returns for hepatic follow-up, the site should use the 800 series as the visit designation.

^a The eligibility period of the prospective baseline assessment will last from 30 to 40 days. Investigators and patients may have up to an additional 5 days to schedule their Visit 3 appointment (beyond the 40 days); however, eligibility will be based on the 30- to 40-day period.

^b Visit is to include a review of any spontaneously reported adverse events and collection of blood samples for immunogenicity, PK, and CGRP plasma.

^c A neurological exam will be conducted at screening, Month 3 (final visit of double-blind treatment), Months 6, 9, and 12 (open-label treatment), and Month 16/early termination in order to assess for any signs of pre-existing or treatment-emergent neurological abnormalities such as stroke or other cerebrovascular events.

^d Electrocardiograms (ECGs) will be performed at Visit 1, Visit 3, Visit 7, Visit 10, Visit 16, and Visit 18 or early termination. Note: The Visit 3 ECG should be collected prior to blood draws and dosing. Patients must be supine for approximately 5 to 10 minutes before ECG collection and remain supine but awake during ECG collection.

^e Vital signs taken at every office visit will include body temperature, blood pressure and pulse. Blood pressure and pulse will be measured in triplicate in the sitting position and should be measured prior to blood draws. Blood pressure will be assessed by utilizing a calibrated machine.

^f Chemistry labs collected at Visit 3, Visit 7, Visit 10, Visit 13, Visit 16, and Visit 18 or early termination must be fasting. Fasting is defined as no food or drink, except water, for at least 8 hours prior to testing.

g In the event of a positive urine leukocyte esterase result, a repeat urine sample will be collected and shipped to the central laboratory.

^h A positive urine test must be followed by a serum pregnancy test for confirmation.

Immunogenicity and storage sample, and PK blood sampling to be performed at the indicated visits and prior to dose administration if the visit is a dosing visit. Samples will be taken in the event of early termination. Immunogenicity samples also may be collected in the event of a systemic allergic/hypersensitivity reaction (see Section 8.4.3). The exact date and time of the samples should be recorded.

Patients will receive injections of placebo or LY2951742 after all other visit procedures are completed. Following the first double-blind dose at Visit 3 and the first open-label dose at Visit 7, patients will be observed for at least 30 minutes in the office.

^k Questionnaire administered by clinician to assess other chronic pain conditions.

¹The C-SSRS, and SHSF (and SHFU when applicable) will be completed at scheduled and unscheduled office visits.

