5.1. Inclusion Criteria

Patients are eligible to be included in the study only if they meet all of the following criteria at screening:

Patient and Disease Characteristics

- [1] Patients are 18 to 65 years of age (inclusive) at the time of screening.
- [2] Have a diagnosis of chronic migraine as defined by the IHS ICHD-3 beta guidelines (1.3) (ICHD-3 2013), that is, a headache occurring on 15 or more days per month for more than 3 months, which has the features of migraine headache on at least 8 days per month.
- [3] Migraine onset prior to age 50.
- [4] Prior to Visit 1, a history of at least 1 headache-free day per month for the past 3 months.
- [5] From Visit 2 to Visit 3 (prospective baseline period), have a frequency of at least 15 headache days, of which at least 8 must have the features of migraine headache (see definitions in Table CGAI.2). To avoid biased reporting, patients must not be told the number of migraine headache days on which study qualification is based.
- [6] From Visit 2 to Visit 3 (prospective baseline period), have at least one headache-free day.
- [7] From Visit 2 to Visit 3 (prospective baseline period), must achieve sufficient compliance with ePRO daily headache entries as demonstrated by completion of at least 80% of daily diary entries.

Informed Consent and Patient Agreements

- [8] Are able and willing to give signed informed consent.
- [9] Are reliable and willing to follow study procedures, including all follow-up visits.
- [10] Women of child-bearing potential must test negative for pregnancy at the time of enrollment based on a serum pregnancy test.

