Appendix 3. Clinical Laboratory Tests

Laboratory Tests Performed during the Study

Hematology: Clinical Chemistry: Serum Concentrations of:

Hematocrit Sodium

Erythrocyte count (RBC) Potassium

Mean cell volume Total bilirubin

Mean cell hemoglobin concentration Direct bilirubin
Leukocytes (WBC) Alkaline phosphatase

Neutrophils, segmented

Alanine aminotransferase (ALT)

Agnorate aminotransferase (AST)

Lymphocytes Aspartate aminotransferase (AST)
Monocytes Blood urea nitrogen (BUN)
Eosinophils Creatinine

Basophils Uric acid
Platelets Calcium

 HbA_{1c} Glucose (fasting)^b

Albumin

Urinalysis:Creatine kinase (CK)Specific gravityTriglyceridespHTotal cholesterolb

Protein HDL^b

Glucose
Ketones Insulin (fasting)
Blood C-peptide (fasting)

Urine leukocyte esterase^a
Microscopic analysis^a

Urine culture^a PK Sample (LY2951742 serum concentration determination)
Immunogenicity

Urine Drug Screen^c

Pregnancy Test (females only)^c
Serum pregnancy or FSH
Urine pregnancy test (local)

Stored Samples
Biomarker Storage

CCI RNA

Abbreviations: FSH = follicle-stimulating hormone; HbA1c = hemoglobin A1c; HDL = high density lipoprotein; PK = pharmacokinetic; RBC = red blood cells; RNA = ribonucleic acid; WBC = white blood cells.

- A positive urine leukocyte esterase result will require a follow-up sample with microscopic analysis and possibly a urine culture.
- Fasting laboratory samples will be collected as shown in the Schedule of Activities (Appendix 2). Fasting is defined as no food or drink, except water, for at least 8 hours prior to testing. All other samples may be collected on a nonfasting basis.
- ^c May be repeated during the study at the discretion of the investigator.

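### Visit 7, the first open-label 240 mg dose, is the only one of 12 dosing visits without the local urine pregnancy test, and nothing requires its same-day serum result before the injection

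*Protocol*

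**What the plan says.** The evidence is in the two tables of the protocol's Appendix 2 (Schedule of Activities) and their footnotes.

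- **Study drug.** Doses fall at Visits 3, 5 and 6, at Visit 7 (marked "X (if continuing to OLE"), and at Visits 8 to 15. Protocol 4.1 sets the Visit 7 dose at 240 mg for everyone entering the extension.
- **Serum test.** The row "Serum Pregnancy (for women of childbearing potential) or FSH at V1 (all other female patients" is marked at Visits 1 and 7 and, in the second table, at Visits 16, 18 and early termination.
- **Urine test.** It is marked at Visits 3, 5 and 6 in the first table, with Visit 7 blank. In the second table ("Urine pregnancyh", where the final letter is the footnote mark) it is marked at Visits 8 to 15.
- **Footnote h.** "A positive urine test must be followed by a serum pregnancy test for confirmation".
- **Study-drug footnote (j).** "Patients will receive injections of placebo or LY2951742 after all other visit procedures are completed".
- **Appendix 3.** The urine test is listed as "Urine pregnancy test (local"); the serum test has no such label.
- **Protocol 5.1, criterion 10.** "Women of child-bearing potential must test negative for pregnancy at the time of enrollment based on a serum pregnancy test". This is the only rule that ties a negative pregnancy result to a study step, and it concerns enrollment.

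**The concern.** At the other 11 dosing visits a local test is done before the injection, so the site can have an answer in hand. At Visit 7 the only scheduled test is serum, and the plan does not say that its result must be known before the dose. The study-drug footnote fixes the order of procedures: blood is drawn first, then the injection is given. It does not make the injection wait for the laboratory.

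Visit 7 is also where the question matters most after Visit 3, because it is the first active exposure for the patients randomized to placebo. Protocol 4.3 equates 5 months with about 5 elimination half-lives, a half-life of about 1 month, so exposure cannot be undone quickly by stopping. Women from the active arms are already exposed and could be spared only a further dose.

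**Working it through.** **1. Number of dosing visits.** Protocol 6.1 gives 3 double-blind and 9 open-label dosing visits, 3 + 9 = 12. SAP 5.5.5 lists Visit 3 plus Visits 5 to 15, which is 1 + 11 = 12. The schedule gives the same 12.

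**2. Tests set against doses.**

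| Row | Visits | Dosing visits covered |
|---|---|---|
| Study drug | 3, 5, 6, 7, 8 to 15 | 12 |
| Urine pregnancy | 3, 5, 6, 8 to 15 | 11 |
| Serum pregnancy | 1, 7, 16, 18, early termination | 1 (Visit 7) |

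The one dosing visit without urine is Visit 7, and it is also the one dosing visit with serum. The serum row otherwise falls at screening, end-of-phase and exit visits. Visit 7 is both the end of the double-blind phase and the first open-label dosing visit, and it received only the end-of-phase test.

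**3. Is the serum result available in time?** The documents do not settle this. Three things point towards a later result: only the urine test is marked local in Appendix 3; Appendix 2 footnote g sends repeat urine samples to a central laboratory; and protocol 10.2.1 refers to "Data managed by a central vendor, such as laboratory test data or ECG data". These are suggestive, not conclusive, since 10.2.1 is about where data are held, not turnaround.

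**4. Age of the latest result if serum is not back.** Visit 6 to Visit 7 is 30 ± 2 days, so the Visit 6 urine result is 28 to 32 days old.

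**5. Size.** Inputs from SAP 5.2: 1140 patients, half on placebo (570), 15% discontinuation. Assumptions not in the documents: 80% to 100% of those reaching Visit 7 enter the extension; 40% to 70% are women of childbearing potential; 1% to 10% per year become pregnant despite contraception.

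- Former placebo patients reaching Visit 7: 570 × 0.85 = 484.5.
- Former placebo women dosed: from 484.5 × 0.80 × 0.40 = 155 to 484.5 × 1.00 × 0.70 = 339.
- Pregnancies newly detectable over 30 days: from 155 × 0.01 × 30/365 = 0.13 to 339 × 0.10 × 30/365 = 2.8.
- At 5% per year: from 155 × 0.05 × 30/365 = 0.64 to 339 × 0.05 × 30/365 = 1.4.

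If serum results are back during the visit, the figure is 0. A similar number of women from the active arms are dosed at Visit 7, but they are not counted because they are already exposed.

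**The case against.** The strongest reply is that no dosing visit goes untested. Each of the 12 has exactly one scheduled pregnancy test, and Visit 7 has the better one: serum is the test used for eligibility and for confirming a positive urine result. The comparison with Visit 3 is also imperfect. The serum test before Visit 3 is taken at Visit 1, which the visit windows place 33 to 90 days earlier (3 + 30 to 45 + 40 + 5), so a same-day urine test is plainly needed there. The plan is silent on serum turnaround, but it leaves other operational detail to manuals and sponsor instructions. And no visit after enrollment has an express rule that the result be negative before dosing, so Visit 7 is not unusual in that respect.

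All of this is correct, and it limits the point. What Visit 7 alone lacks is a local test, not a stated rule, and the harm is conditional on the serum result arriving after the visit. The numbers also give no credit for a missed period, self-report or a discretionary test, and 28 to 32 days is the planned window; the SAP's deviation table tolerates dosing intervals of 21 to 37 days.

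The other safeguards do not close the gap. Contraception (criterion 11) lowers the number of cases, yet the sponsor still tests at the other 11 dosing visits. The repeat test in Appendix 3 footnote c is optional. Discontinuation for pregnancy (7.1.1), reporting through the SAE process (8.2.1) and the SAP deviation for women with a positive test who are not discontinued all act once the pregnancy is known, which here would be after the dose.

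**Conclusion.** The concern holds as a minor patient-safety point. The schedule gap is certain: 11 of 12 dosing visits have the local urine test, and Visit 7 does not. Whether it has consequences depends on a fact that the documents do not give, namely whether the serum result is back before the injection. If it is, there is no gap. If it is not, the expected number of newly detectable pregnancies first exposed at Visit 7 among former placebo patients is about 0.1 to 2.8, resting on the three assumed inputs above. No endpoint, sample size, power or error rate is touched. Confidence is medium because of the unstated turnaround. The change is still worth making, because it removes the dependence on that turnaround at little cost.

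**What to change.** In Appendix 2, mark the local urine pregnancy test at Visit 7 for women of childbearing potential who continue into the open-label extension. Apply it in all arms, since treatment assignment stays blinded. Keep the Visit 7 serum test; it can also serve as the confirmation that footnote h asks for after a positive urine result. Coverage then becomes 12 of 12 dosing visits.

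Optionally, if the sponsor wants a rule that the result be negative before the injection, attach it to the urine row in both tables, for example by extending footnote h, so that it applies at every dosing visit and not at Visit 7 alone.

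The cost is one schedule cell, made through a protocol amendment and best carried with the next one, plus one urine test per continuing woman of childbearing potential. With 1140 × 0.85 = 969 patients reaching Visit 7, that is 969 × 0.80 × 0.40 = 310 to 969 × 1.00 × 0.70 = 678 tests under the same assumptions. Urine is already collected at Visit 7 for urinalysis, and sites already run this test at the other dosing visits. If the optional rule is adopted, a false-positive urine result would delay that dose until serum confirmation.
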